### 4.4.1 Screen Failure

If a subject is termed as a screen failure for not meeting the inclusion/exclusion criteria, the subject may be rescreened only after obtaining Sponsor approval. The Sponsor may approve for rescreening those cases in which subjects failed the screening parameters within a narrow

PAGE 32 OF 80

margin. Screening laboratory tests may be repeated following the approval of the Sponsor or its designee if the laboratory test results seem implausible or inaccurate.

At least 35 days from the date of the subject's initial screening will need to elapse prior to rescreening a subject. The subject will need to be rescreened under a new screening number and a new informed consent must be obtained. A screen failure occurs when a patient who has signed the informed consent form (ICF) does not meet all the entry criteria outlined in this protocol and has not been randomized or received study drug. No study procedures (including End-of-treatment procedures) will be performed for these patients. For patients who fail to meet the inclusion criteria or who meet 1 or more of the exclusion criteria, the PI (or designee) will document on a screening log the reason for the screening failure.

### 4.5 HANDLING OF SUBJECT WITHDRAWAL

In case of withdrawal of consent, and unless otherwise stated by the subject in the withdrawal of consent, PI(s) will be encouraged to obtain information from the subject in order to follow the medical status of the subjects (especially when the subject withdraws his/her consent after having experienced an AE/SAE or an efficacy endpoint). Principal Investigator or designee(s) must make reasonable attempts (at least 3 attempts, one of which will be via a certified/traceable mail) to contact subjects that are lost to follow-up, in order to obtain health status and reason for withdrawal. These attempts must be documented in the medical records. In addition, if patient withdraws from the study, any data collected during the period of time will maintained as part of the study data.

Approved by: [name] [name] Protocol No.: SARO.17.010

CONFIDENTIAL
PAGE 33 OF 80

### 5 STUDY TREATMENTS/IP MANAGEMENT

Saroglitazar magnesium 4 mg will be administered orally once daily (OD) in the morning 60 minutes before breakfast without food, for a period of 24 weeks.

### 5.1 TREATMENTS TO BE COMPARED

[figure not shown]
### 5.1.1 Investigational Product Description

The investigational product (IP) is Saroglitazar magnesium, which will be formulated as tablets, and will contain 4 mg of Saroglitazar magnesium and excipients.

The product that will be used in this study is outlined in Table 2.

**Table 2 Identity of Study Drugs** 

Saroglitazar Tablet 4 mg Oral Magnesium	

### 5.1.2 Comparator Drug Description

Not Applicable.

#### 5.2 DOSAGE AND TREATMENT SCHEDULE

Saroglitazar magnesium 4 mg will be given once daily orally in the morning 60 minutes before breakfast without food, for 24 weeks. However, on the day of the scheduled clinical visit, subjects will have the IP administered on site after fasting blood sample collection. If on the

Approved by:	Protocol No.: SARO.17.010
[name] [name]	Version No.: 7.0

CONFIDENTIAL

**PAGE 34 OF 80** 

day of a scheduled clinic visit the subject has already taken the IP, all procedures except blood sample collections will be performed. The subject will be asked to return in fasting condition the next day to have the blood sample collected, and will be reminded not to take the IP until after the blood sample collections. If the subject again returns having taken the IP, blood samples will be collected and the subject will be asked to return for the next scheduled visit.

### 5.3 PACKAGING, LABELLING AND SUPPLY

Γablets of Saroglitazar magnesium 4 mg will be packed, labeled and supplied by the Sponso	Эr
according to all local legal requirements.	
. Th	ne

investigator designee will confirm the receipt of IP in writing via fax/email.

The PI or designee will maintain an accurate record of the receipt of the study drug, including the dates received. Unused drug supplies will be returned to the Sponsor (or designee) for destruction/destroyed at the site after approval for the same by the Sponsor. No study drug will be destroyed or returned until complete drug accountability has been performed by the study monitor. All supplies must be accounted for at the end of the study period.

Investigational product must be dispensed to each subject in such a way that the subject can take the doses in accordance with the Protocol. A Drug Accountability Log(s) for recording the receipt, dispensing and return of the IP must be maintained by the PI or any designated personnel. The Drug Accountability Log(s) must be kept up to date and must be made available to the study monitor during monitoring visits.

### 5.4 STORAGE CONDITIONS AND STABILITY

Saroglitazar magnesium tablets will be stored at room temperature (20°C to 25°C or 68°F to 77°F) in a dry place away from light at the study site or pharmacy. If the IP temperature extends outside the 20-25°C range, a temperature excursion must be documented in the study-specific temperature log, and sent to the Sponsor. If the excursion is within 15-30°C, quarantine is not required, and the IP is acceptable for use. If the excursion is outside of the 15-30°C range, the IP must be quarantined until a decision on the stability of the IP is made by the Sponsor. If the excursion goes beyond the range of 15-30°C it will be considered as a

CONFIDENTIAL

**PAGE 35 OF 80** 

protocol deviation. Protect the IP from light. All IP supplies in the study will be stored in a secure location with access limited to the Site Pharmacist or the PI designated site staff.

#### 5.5 BLINDING

This is an open-label study, therefore, PI and participants will be made aware what treatment they will be administered.

#### 5.6 METHOD OF ASSIGNING SUBJECTS TO TREATMENT GROUP

All subjects will receive Saroglitazar magnesium 4 mg. A screening number will be assigned at the site and will be used to identify the subject throughout the study and will be entered on all documentation. The Screening Number will be assigned in numerical order at the site. A subject number will not be assigned to more than 1 subject. If a subject is not eligible to receive treatment, or if a subject discontinues from the study, the Screening Number cannot be assigned to another subject.

Subjects will be considered randomized as soon as the first allocation treatment number/drug kit is assigned. The first study drug intake should take place as soon as possible after randomization (on the same day), under medical supervision. In the event a subject is randomized but is not administered study drug, this will be considered an early termination, not a screen failure. The randomization number and subject drug kit will not be reassigned to another subject.

### 5.7 SELECTION OF DOSES

Saroglitazar magnesium 2 and 4 mg have favorably modified the lipid profile and glycemia in the dyslipidemic patients with or without diabetes mellitus during its development in Phase 2 and 3 studies. Considering the efficacy, safety and tolerability of Saroglitazar magnesium, it is approved in India at the doses of 2 mg and 4 mg QD for the treatment of "Diabetic Dyslipidemia" and "Hypertriglyceridemia with T2DM not controlled by statin therapy". Saroglitazar magnesium 4 mg dose has shown favorable effects on lipid profiles and on liver enzyme levels, therefore, this dose has been selected for this study.

### 5.8 CONCOMITANT MEDICATION

1. Standard of care for patients with LT will be allowed. These include management of immunosuppression per site's transplant related protocol. Additionally,

PAGE 36 OF 80

management of metabolic co-morbidities such as diabetes, hypertension, hyperlipidemia and obesity will also be done as per local standard of care.

2. Patient with stable doses of statins (simvastatin, pravastatin, atorvastatin, fluvastatin, lovastatin, and rosuvastatin) or fibrates (clofibrate, fenofibrate) will be allowed in the study; however, their doses should remain stable throughout the study period.

### 5.8.1 Subjects on concomitant anti-diabetic medication

Patients on anti-diabetic medication must be assessed at scheduled visits for hyperglycemia/hypoglycemia; rescue medication will also be permitted, if required.

Patients on concomitant anti-diabetic medication will be provided with a glucometer and instructions for use. All point-of-care (POC) glucose measurements collected/documented by patients during the study period must be performed on the study-provided glucometer. The investigational site will download/record the data from glucometer/patient diary for assessment of glucose levels from the previous visit.

The patients should monitor their glucose levels as follows:

- Fasting blood glucose should be measured on at least two different days in a week. These measurements should be done in the morning before having breakfast and when the patient has been fasting for a minimum of 10 hours.
- Spontaneous measurements of blood glucose should be done in the event the patient suffers from suspected hypoglycemia. The PI or designee should inform the patients on recognizing the symptoms of hypoglycemia (i.e. palpitations, tremor, diaphoresis, hunger and/or cognitive impairment) and instruct them on the actions to be taken in accordance with standard-of-care.

The American Diabetes Association (ADA) recommends the following treatment for non-severe hypoglycemia during which a patient is willing and able to consume oral treatment:

- 1. Consume 15-20 grams of glucose or simple carbohydrates
- 2. Recheck your blood glucose after 15 minutes
- 3. If hypoglycemia continues, repeat #1 & #2
- 4. Once your blood glucose returns to a normal level, consume a small snack if your next planned snack or meal is greater than 1 hour in the future.

Approved by: Protocol No.: SARO.17.010
[name] [name] Version No.: 7.0

PAGE 37 OF 80

Examples provided by the ADA of items containing 15 grams of simple carbohydrates include:

- Glucose tablets (follow instructions on the package)
- Gel tube (follow instructions on the package)
- 2 tablespoons of raisins
- 4 ounces (1/2 cup) of juice or regular (non-diet) soda
- 1 tablespoon of sugar, honey or corn syrup
- 8 ounces of nonfat or 1% milk
- Hard candy, gumdrops or jellybeans (read package for amount to consume)

In the event of severe hypoglycemia when a patient is unconscious and possibly seizing, and/or unable to safely ingest carbohydrates, do not attempt oral treatment. If glucagon is available, this should be administered as soon as possible. If glucagon is not available, it is not able to be administered or persons witnessing the event do not feel able to handle the situation, emergency medical personnel should be summoned via calling 911.

Principal Investigator will advise patients to report all hypoglycemic episodes occurring during the course of the study as they will be recorded in the electronic Case Report Form (eCRF).

Treatment for such conditions should be initiated as soon as the need for treatment is identified by the PI, in accordance with treatment guidelines and standard of care, and should be adjusted as necessary to treat the patient's condition(s). All treatment with these drugs must be recorded in the eCRF.

#### 5.9 STOPPING RULE(S)

Safety and tolerability will be evaluated by the incidence, severity, and relationship to study intervention of any AEs and changes from baseline in laboratory test results, physical examination findings, and vital sign measurements, at any time after the subject has received study intervention. If continuous safety analysis reveals an adverse trend, the PI may halt the study independently, or in consultation with the IRB/Sponsor, as appropriate. Furthermore, if three or more subjects develop the same SAE related to the IP or a procedure, the study will be suspended until the safety review outcome, in consultation with the IRB/Sponsor.

Approved by: Protocol No.: SARO.17.010
[name] [name] Version No.: 7.0

CONFIDENTIAL
PAGE 38 OF 80

### 5.9.1 Discontinuation of Patients from the Study Drug

- Discontinue patient with an AE of CTCAE grade 3 or higher that is possibly or probably related to IP and discontinue patient with an AE of CTCAE grade 4 regardless of attribution to IP.
- 2 If any of the following criteria are met, the patient must be immediately discontinued from IP and followed until resolution of adverse events and laboratory values return to baseline/stable:
  - a. Total Bilirubin ≥3.0 mg/dL.
  - b. Total CK >5 X ULN.
  - c. Amylase or lipase >ULN.
  - d. eGFR <60 mL/min/1.73 m^2 and where the value is reconfirmed after 24 hours repeat. Additionally, any subject who requires renal replacement therapy should also be discontinued from IP.
  - e. Hemoglobin <10 mg/dL or hematocrit <30%; platelets <100,000/ $\mu$ L; WBC <4 x  $10^3/u$ L.
  - f. If troponin and CK-MB exceed the 99th percentile of the upper reference limit of the particular assay, serial labs should be obtained along with serial 12-lead ECGs, and cardiology should be consulted. If a patient has symptoms of dyspnea, edema, or a presumptive diagnosis of heart failure, NT-proBNP should be measured as close to the event as possible.
- 3 The criteria for discontinuing or temporarily interrupting study drug with close monitoring are as follows:
  - a. When the baseline measurements (BLM) are <2x ULN, discontinue if ALT or AST increases to >5x BLM.
  - b. When the BLM ≥2X ULN but <5X ULN, discontinue if ALT or AST increases to >3X BLM.
  - c. When BLM  $\geq$ 5X ULN, discontinue if ALT or AST increases to  $\geq$ 2X BLM.
  - d. For ALT or AST increases to >2X BLM accompanied by a concomitant total bilirubin increase to >2X BLM OR an INR increase by >0.2.

PAGE 39 OF 80

- e. For elevations of liver enzymes accompanied by symptoms consistent with hepatic injury [e.g., fatigue, nausea, vomiting, right upper quadrant pain or tenderness, fever, rash, and/or eosinophilia (>5%)].
- f. Temporarily interrupted treatment should be permanently discontinued for recurrence of laboratory abnormalities or symptoms following re-challenge.
- g. If a patient lives in a remote area, testing can be performed locally and the results communicated to the PI/site promptly.
- h. If patients develop elevations of AST or ALT >2 times baseline measure or total bilirubin >1.5 times BLM while on study, testing should be repeated within 48 to 72 hours. Persistent elevations should be followed by repeat testing and physical examination 2-3 times per week with or without drug discontinuation.

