### Discontinuation of patients from the Study Drug

- Discontinue any patient with an AE of Common Terminology Criteria for Adverse Events (CTCAE) grade 3 or higher that is possible or probably drug related and discontinue any patient with an AE of CTCAE grade 4 regardless of attribution to study drug.
- If any of the following criteria are met, the patient shall be immediately discontinued from drug and followed until resolution of adverse events and laboratory values shall be returned to baseline.
  - a. Total bilirubin ≥3.0 mg/dL.
  - b. Total CK >5 X ULN.
  - c. Amylase or lipase >ULN.
  - d. eGFR <60 mL/min/1.73 m^2 and where the value is reconfirmed after 24 hours repeat. Additionally, any subject who requires renal replacement therapy should also be discontinued from drug.
  - e. Hemoglobin <10 mg/dL or hematocrit <30%; platelets <100,000/ $\mu$ L; WBC <4 x  $10^3$ /uL.
  - f. If troponin and CK-MB exceed the 99th percentile of the upper reference limit of the particular assay, serial labs should be obtained along with serial 12-lead ECGs, and cardiology should be consulted. If a patient has symptoms of dyspnea, edema, or a presumptive diagnosis of heart failure, NT-proBNP should be measured as close to the event as possible.
- 3 The criteria for discontinuing or temporarily interrupting study drug with close monitoring are as follows:
  - a. When baseline measure (BLM) are <2x ULN, discontinue if ALT or AST increases >5x BLM.
  - b. When the BLM ≥2X ULN but <5X ULN, discontinue if ALT or AST increases >3X BLM.
  - c. When BLM ≥5X ULN, discontinue if ALT or AST increases >2X BLM.
  - d. For ALT or AST increase >2X BLM accompanied by a concomitant total bilirubin increase to >2X BLM OR an INR increase by >0.2.

Confidential Page 9 of 80

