### 4.4 WITHDRAWAL CRITERIA

The Investigator may withdraw a subject from the study for any of the following:

- 1 Subject who reports an SAE and if considered in Investigator or Medical Expert's opinion it is not in the subject's best interest to continue.
- 2 Any subject found to have entered the study in violation of the protocol.
- 3 Termination of the study by the Sponsor or Principal Investigator (PI) or the regulatory authorities or Independent Ethics Committee/Institutional Review Board (IEC/IRB).
- 4 The subject is lost to follow-up.
- 5 Any subject who wishes to withdraw his/her consent for participation in the study.
- 6 In case a subject becomes pregnant, then she will be withdrawn from the study.

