#### 6.2.10 Abnormal Laboratory Findings

In addition, a clinically significant value outside the normal or reference range in a routine safety assessment, such as clinical laboratory, vital signs or standard 12-lead ECG, and 2D ECHO may signify an adverse finding. Additional examinations or repetition of test will be performed as medically indicated.

If the PI considers the abnormality as of major medical relevance, he/she should also record this as an AE. If the findings contribute to a clinical diagnosis (e.g. hepatitis in case of increased liver enzymes), this diagnosis should be recorded as an AE.

The criteria for determining whether an abnormal objective test finding should be reported as an AE are as follows:

- 1. The test result is associated with accompanying symptoms, and/or
- 2. The test result requires additional diagnostic testing or medical/surgical intervention, and/or
- 3. The test result leads to change in study dosing or discontinuation from the study, significant additional concomitant drug treatment or other therapy, and/or
- 4. The test result leads to any of the outcomes included in the definition of an SAE, and/or
- 5. The test result is considered to be an AE by the PI or designee.

For any abnormal test result that meets one of the above conditions except for the last condition, the PI or designee will provide a justification in the source documentation for not reporting the abnormal test finding as an AE.

Each AE shall be evaluated for severity, seriousness, duration, resolution, action taken and its association with the study treatment. The participant may be withdrawn or terminated from the study depending on the seriousness of the AE(s).

CONFIDENTIAL
PAGE 51 OF 80

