#### **Causality**

For all AEs, the PI or designee will provide an assessment of causal relationship to study drug. The causality assessment must be recorded on the appropriate AE reporting page of the patient's eCRF.

Causal relationship will be classified according to the following criteria:

Unrelated

PAGE 70 OF 80

- Possibly related: Suggests that the association of the AE with the study drug is unknown. However, the AE is not reasonably supported/explained by other conditions.
- Probably related: Suggests that a reasonable temporal sequence of the AE with study drug administration exists and, based upon the PI's clinical experience, the association of the AE with study drug seems likely.
- Definitely related: Suggests that a causal relationship exists between the study drug and the AE, and other conditions (concomitant illness, progression or expression of the disease state, reaction to concomitant medication) do not appear to explain the AE.
- Unknown

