#### 9.4.5 Expected Adverse Events

Adverse events reported by 2% or more patients treated with Saroglitazar magnesium during the double-blind, active-controlled study with pioglitazone as the comparator regardless of causality included gastritis and asthenia. In the double-blind placebo controlled study, AEs reported by 2% or more patients treated with Saroglitazar magnesium included gastritis, dyspepsia, pyrexia and pain. The details of AE(s) experienced during the Saroglitazar magnesium studies are mentioned in the IB. Principal Investigator(s) are advised to provide protocol education for patients and caregivers for potential symptoms of adverse effects that should be reported to the site/PI, such as skeletal muscle pain, weight gain, peripheral edema, shortness of breath, hypoglycaemia, etc.

CONFIDENTIAL
PAGE 71 OF 80

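### The mandatory Grade 3 drug stop names possibly and probably related events but omits the protocol's strongest causality category, definitely related

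*Protocol*

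**What the plan says.** Protocol section 5.9.1, item 1, sets the individual drug stop by grade and causality: "Discontinue patient with an AE of CTCAE grade 3 or higher that is possibly or probably related to IP". The same item requires a stop for any Grade 4 event, whatever its attribution. The synopsis, under discontinuation from the study drug, has the same pair of categories: "grade 3 or higher that is possible or probably drug related".

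Section 9.4.4 (Causality) tells the investigator to classify every AE on a five-category scale and record the result in the eCRF. The categories are *Unrelated*, *Possibly related*, *Probably related*, *Definitely related* and *Unknown*. The strongest has its own definition: "Definitely related: Suggests that a causal relationship exists between the study drug and the AE".

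Items 2 and 3 of section 5.9.1 add stops or interruptions that do not depend on causality. They rest mainly on laboratory and liver findings: bilirubin, CK, amylase or lipase, eGFR, hematology, and ALT/AST with or without other signs.

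**The concern.** The rule obliges the site to stop drug when causation is possible or probable, and does not mention the case where causation is regarded as established. The scale makes the rater choose one label, so an event recorded as *Definitely related* is not also recorded as *Probably related*. Taken at its word, the rule binds on weaker evidence of harm and is silent on the strongest.

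Two things depend on it. One is the protection of the individual patient, in a trial whose primary endpoint is safety. The other is deviation classification. The synopsis and section 7.4 both count as a deviation a patient who met the discontinuation criteria but stayed in the study. On a literal reading, continuing after a possibly related Grade 3 event could be classified under that item, while continuing after a definitely related one could not.

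**Working it through.** The plan gives no figure to reproduce and no event rate, and none is assumed here. The check compares the stop rule with the causality scale and then looks for another mandatory rule that closes the gap.

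**Step 1. Apply item 1 of section 5.9.1 to each category in section 9.4.4.**

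| Causality rating | Grade 3 AE | Grade 4 AE |
|---|---|---|
| Unrelated | no stop (as intended) | stop |
| Possibly related | stop | stop |
| Probably related | stop | stop |
| Definitely related | not named | stop |
| Unknown | not named | stop |

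Three of the five categories attribute the event to study drug, and the rule names two of those three. The omission occurs in two places, the synopsis and section 5.9.1. Neither document contains a sentence that turns the pair into a floor.

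**Step 2. Find a case that items 2 and 3 do not catch.** Section 9.4.5 lists effects that patients should be taught to report, "such as skeletal muscle pain, weight gain, peripheral edema, shortness of breath, hypoglycaemia". The clearest uncovered case is Grade 3 skeletal muscle pain with CK not above 5 times ULN. Peripheral edema is a second example but a less clean one. Item 2f mentions edema under the immediate-stop heading, although its text only calls for NT-proBNP to be measured.

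**Step 3. Check the other individual provisions.** Section 4.4 is permissive: "The Investigator may withdraw a subject from the study for any of the following". Its AE-related item is limited to SAEs and turns on opinion. Section 6.2.10 likewise allows, but does not require, withdrawal according to how serious the AE is. Neither is a mandatory drug stop.

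**Step 4. Check the study-level provisions.** The counted triggers that a Grade 3 event could reach are:

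- Section 5.9: suspension "if three or more subjects develop the same SAE related to the IP or a procedure".
- Section 5.9.2: the same Grade 3 AE in three patients, as a condition that may warrant termination.
- Section 7.5: at least three treatment-related AEs of Grade 3 or higher, for an ad hoc DMC meeting.

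For the two counts based on patients, 3 / 15 = 20% of planned enrolment. A single definitely related Grade 3 event reaches none of the three. Sections 5.9 and 5.9.2 also allow uncounted discretion, and section 7.5 provides for regular DMC review. All of these act on the study and do not take one patient off drug.

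**Step 5. Infer the intent.** Sections 5.9 and 7.5 speak simply of related or treatment-related events, which includes *Definitely related*. Among these rules only the individual stop lists causality categories, and its list is incomplete.

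**The case against.** The best reply is that the gap exists only on a very literal reading. A rule that stops drug for possible causation plainly covers established causation, and an event meeting the definition of *Definitely related* would ordinarily meet that of *Probably related* too. The text lists cases that oblige a stop; it does not say that drug continues in the others. The exposed case is also narrow. The event must be exactly Grade 3, must miss every criterion in items 2 and 3, and must be rated *Definitely related*. That rating is demanding in an uncontrolled study of transplant recipients on immunosuppression, some also on statins or fibrates. No result depends on it.

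Most of this stands as an argument about weight. The intent is evident, continued dosing would be an unreasonable reading, and the 20% describes the study-level triggers, not the size of the defect. It does not remove the omission: the protocol defines the categories as separate, and no other mandatory individual rule covers the case.

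**Conclusion.** The concern holds and is minor. The mandatory Grade 3 drug stop leaves out one of the three categories that attribute an event to study drug, the strongest, in both places where the rule appears. It is a drafting error with a clear intended meaning, but it is wrong as written: it mandates the stop on weaker attribution and not on the strongest. The conclusion rests on the wording alone and on raters recording a single category per event. How often the case would arise cannot be estimated from the documents. An investigator would very likely stop drug in any event, and no analysis in the protocol or SAP is affected.

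**What to change.** In section 5.9.1, item 1, and in the matching synopsis item, write possibly, probably or definitely related to IP.

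Optionally, add one sentence on how a Grade 3 event rated *Unknown* is handled. Section 9.4.4 opens its middle category with "Possibly related: Suggests that the association of the AE with the study drug is unknown", which comes close to the separate *Unknown* rating. Its next sentence, on the lack of another reasonable explanation, does help to tell them apart. This addition is a clarification and the main correction does not depend on it.

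The cost is one added word in two places, plus the optional sentence, carried in the next protocol amendment. No procedure is added and the SAP is unchanged.
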